## GLOSSARY OF TERMS AND ABBREVIATIONS

[figure not shown]
AE	Adverse Event
ANC	Absolute Neutrophil Count
APR	Annual Progress Report
AST	Aspartate aminotransferase
CI	Chief Investigator
ECOG	Eastern Cooperative Oncology Group
eCRF	Electronic Case Report Form
EU	European Union
FBC	Full Blood Count
GCP	Good Clinical Practice
HTA	Human Tissue Authority
ICF	Informed Consent Form
ICH	International Conference on Harmonisation
IF	Immunofluorescence
ISF	Investigator Site File
NCI-CTCAE	National Cancer Institute Common Toxicity Criteria For Adverse Events
NRES	National Research Ethics Service
ORR	Overall response rate
OS	Overall survival
PD-(L)1	Programmed death (ligand) 1
PFS	Progression free survival
PI	Principal Investigator
PIS	Patient Information Sheet
REC	Research Ethics Committee
RNASeq	RNA sequencing

SAE	Serious adverse event
SAR	Serious adverse reaction
SDV	Source data verification
SOP	Standard Operating Procedures
SUSAR	Suspected Unexpected Serious Adverse Reaction
TMB	Tumour mutational burden
TMF	Trial Master File
TMG	Trial Management Group
US	Ultrasound
WBC	White blood cell count

## STUDY SYNOPSIS

Title	Prospective E valuation of A I R & D tool for B iology and R esponse in A dult I nvasive N euro-oncology (PEAR-GLIO)
Main Objectives	
The study objectives are concerned with measurements and endpoints collected from laboratory testing on patient-derived primary brain tumours.
 
The primary objective is to establish a functional dose of each FDA-approved therapy for primary solid brain tumours in Pear Bio's ex vivo platform, and to confirm these therapies demonstrate their intended mechanism of action (direct cell killing, cell killing by immune cell activation, etc.) This objective is quantified using intra-patient and inter-patient statistics to evaluate differential ex vivo treatment efficacy for approved glioma therapies.
 
Other objectives include measuring the correlation between multi-omic biomarkers and ex vivo treatment response, and exploring responses to other potential therapies for brain tumours.
 
Our Patient & Public Involvement & Engagement (PPIE) workstream will run in parallel, but will be open to a wider group of people, who may or may not be patients who participate in PEAR-GLIO, and will be managed outside the study.

Phase	N/A
Design	
This is a UK-based, observational study that aims to validate a diagnostic tool on its ability to test therapeutic sensitivity of brain tumours ex vivo. Patients diagnosed with brain tumours will undergo standard of care surgery, and have 40mL of whole blood collected. The blood and tissue material will be shipped fresh. The patient will go through routine post-surgical care and data collection. Any known treatments and events occurring post-surgery, such as the administration of adjuvant therapy or recurrence, will be recorded and communicated to Pear Bio. The samples and data sent to Pear Bio will be used to evaluate the study's objectives.

	
Sample Size	50
Inclusion Criteria	
 
1. Patient diagnosed with operable brain cancer, thought likely to be primary solid brain tumour on imaging (grade 2 - 3 meningioma; grade 1 - 4 tumours otherwise) or with histologically proven primary malignant solid brain tumour;
 
2. Able to give written informed consent prior to admission to this study;
 
3. Female or male aged <math>\geq 18</math> years;
 
4. Patient consents to the use of their surgical sample and 40mL of whole blood for research purposes;
 
5. Surgical sample and yields <math>\geq 0.4g</math> for the study;
 
6. Patient consents to providing histopathology data (e.g., confirmation of histological subtype as oligodendroglioma) and other pseudonymised health information including imaging, treatment and outcome data.
 

Exclusion Criteria	
 
1. Inoperable or biopsy only;
 
2. Suspected lymphoma or myeloma, or grade 1 meningioma
 
3. Preoperative haemoglobin levels below 120g/L;
 
4. Patients who have already received chemotherapy, targeted therapy, immunotherapy, or radiotherapy less than 30 days before date of surgery, unless as part of a clinical trial (requires per-patient sponsor approval).
 
5. Recurrence of cancer originating from a site other than the brain;
 
6. Any other disease, metabolic dysfunction, physical examination finding, or clinical laboratory finding that, in the investigator's opinion, gives reasonable suspicion of a disease or condition that may affect the interpretation of the results, render the patient at high risk from treatment complications or interferes with obtaining informed consent.
 

## 1: INTRODUCTION

### 1.1 Trial outline

Pear Bio have developed a 3D micro-tumour and computer vision platform to culture patient-derived tumour samples and predict sensitivity to various therapeutic agents. This study is intended to validate the mechanism of action of FDA-approved primary brain tumour therapies, such as Temozolomide, Lomustine and Bevacizumab, as well as therapies being assessed in clinical trials, on fresh brain tumours and autologous immune cells isolated from whole blood.

This is a proof of concept study to confirm that therapies used in primary brain tumours can be tested in Pear Bio's platform. Follow-on studies will be used to determine the sensitivity and specificity of Pear Bio's test in predicting patient response (OS and PFS). This study will acquire fresh patient tumour samples and 40 mL of whole blood per patient. Samples will be shipped fresh on the same day of collection to Pear Bio's lab. Histopathology reports will be provided to Pear Bio shortly after the sample shipment in order to confirm the tumour subtype (although samples will not be excluded from analysis based on tumour subtype). Other available patient data, including imaging and imaging reports, will also be provided in a pseudonymised form. Patients who have had previous tissue sampling (i.e. those undergoing treatment for relapsed disease) will also provide information on previous histology and treatment.

Pear Bio will isolate cells from the tumour samples and whole blood, co-culture them into 3D micro-tumours, and run live microscopy-based assays to determine *ex vivo* tumour response to treatments. Image data will be analysed using a proprietary computer vision pipeline to measure *ex vivo* tumour response metrics, such as tumour cell death, tumour cell migration and immune cell infiltration. Molecular biology assays will be conducted to determine changes in DNA features (tumour mutational burden and mis-match repair), gene expression (PCR or RNASeq) and protein distribution (immunofluorescence or spatial proteomics assays) for biomarkers due to *ex vivo* treatment exposure.

Various Pear Bio laboratory assays will be compared to validate cell culture models, computer vision algorithms and drug mechanisms of action. Any available patient data will also be used to determine whether Pear Bio's assays can predict patient outcomes, such as recurrence or eligibility for future targeted therapies. However, due to the variety of patients recruited, the low total sample size, and the lack of evaluable patients receiving non-surgical treatment, no formal statistical analysis will be conducted on patient outcomes.

At the end of this study, Pear Bio will determine whether the platform has potential for patient stratification in primary brain tumours. Future studies will aim to demonstrate the sensitivity/specificity of Pear Bio's platform for an eventual intended use in guiding treatment decision making for patients with primary brain tumours in order to increase their response rates.

Our Patient & Public Engagement & Involvement (PPIE) workstream will hold three meetings and use online questionnaires and consultations to help understand patient, carer, professional and public views on the Pear Bio platform and its use.

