## **2: STUDY AIMS AND OBJECTIVES**

### **2.1 Primary objectives and endpoints**

Primary objective	Endpoints

The primary objective is to establish a functional dose of each FDA-approved therapy for glioma in Pear Bio's ex vivo platform, and to confirm these therapies demonstrate their intended mechanism of action (direct cell killing, cell killing by immune cell activation, etc.)
	
As the primary objective is laboratory-based, a patient outcome endpoint is not necessary. Instead, success will be determined by:
 
 
1. Observing differentiated ex vivo treatment response across the therapies/combos tested on each patient's tumour sample (intra-patient sample comparison)
 
2. Observing differentiated ex vivo treatment response levels between the cohort of samples collected from patients on a per therapeutic/combo basis (inter-patient sample comparison)
 

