### 3.3 Data and tissue collected

	Biospecimens	Data
Required	
 
At least 0.4g of fresh, unfixed, tumour tissue taken from surgery
 
4 x 10mL EDTA vials of matched whole blood
 
	
 
Demographic data (pseudonymised)
 
Redacted pathology reports, including immunohistochemistry tests, molecular pathology and NGS (IDH and MGMT in particular) and further genomic data where available, including methylation profiling
 

		
 
3. Radiology images and reports
 
4. Concomitant medications
 

Collected if available	N/A	
 
1. Blood and liver/kidney function tests at baseline
 
2. Follow-up outcome data, including recurrences
 
3. Follow-up treatment data, including adjuvant therapy regimens
 

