### 3.5 Patient evaluability

In order to be considered evaluable, patients must meet the eligibility criteria, consent to the use of their surgical sample and blood for the study, and yield a research sample with sufficient weight and tumour cell content resulting in the establishment of a successful cell culture in the Pear Bio laboratory.

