  - d. Comparing the general efficacy of the regimens tested across patient samples using regimen efficacy ranks on each sample and using Kendall's W and Spearman ranked correlation tests to determine whether some regimens consistently outperform others *ex vivo* (on a given metric of interest)

- e. Comparing the general efficacy of the regimens tested across patient samples using Repeated Measures ANOVA for each phenotypic *ex vivo* tumour response metric of interest
- f. Comparing the relative efficacy of any 2 regimens tested across patient samples using a paired T-test for each phenotypic *ex vivo* tumour response metric of interest

The primary objective will be met if there are significant variations in intra-patient and inter-patient sample responses. Due to the heterogeneity of glioma treatment response in the clinic, one regimen is not expected to consistently outperform other options across all patient samples in the laboratory. That could indicate *ex vivo* overperformance due to assay conditions that require adjustment, either in the biology workflow or response vs resistance thresholds, before the assay is used in interventional trials to guide treatment decisions.

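### Section 7.2.1 judges inter-patient variation over all tumour types pooled, so differences between tumour types alone can satisfy the inter-patient half of the success rule

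*Combined protocol and SAP*

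**What the plan says.** **Who enters.** Section 4.1 admits tumours that imaging suggests are primary and solid: meningioma of grade 2 or 3, and other types of grade 1 to 4. The section on other primary brain tumours (the second one numbered 1.2.2) adds that rarer types such as ependymoma are eligible. Sections 1.1 and 3.1 also admit previously treated patients having further surgery. Section 4.2 excludes grade 1 meningioma and suspected lymphoma or myeloma.

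**Who is analysed.** Section 1.1 has the histopathology report follow the sample to confirm its subtype, "although samples will not be excluded from analysis based on tumour subtype". Section 3.5 says that, to be evaluable, "patients must meet the eligibility criteria", and section 3.6 replaces those who are not evaluable.

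**What is analysed.** The inter-patient comparisons in section 7.2.1 run over the cohort of samples, one regimen at a time. They consist of groupings of samples by biomarker change or phenotypic response, box plots, Kendall's W and Spearman correlation on ranks, repeated measures ANOVA and paired t-tests. No item carries a tumour-type stratum, covariate or subset. MGMT methylation enters only in the secondary analysis (7.2.2).

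**What counts as success.** "The primary objective will be met if there are significant variations in intra-patient and inter-patient sample responses".

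**Scope wording.** Section 2.1 speaks of "each FDA-approved therapy for glioma"; the synopsis speaks of "each FDA-approved therapy for primary solid brain tumours".

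**Data available.** Section 3.3 makes pathology reports with molecular results ("IDH and MGMT in particular") required data.

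**The concern.** Section 1.1 says that the study will be used to decide whether the platform has potential for patient stratification. Section 1.2.3 gives the clinical gap: known markers predict chemosensitivity in general, but not which therapy suits which patient. For that purpose, the informative variation is between patients whom pathology would put in the same group.

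The inter-patient half of the success rule does not ask for this. If meningioma or ependymoma samples behave differently from glioma samples in culture, the pooled cohort shows inter-patient variation even when patients within each tumour type are indistinguishable. A reader of the final report could not tell an assay that separates patients from one that only separates tumour types.

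**Working it through.** **1. Is there a figure to reproduce?** No. Section 7.1 gives a maximum of 50 evaluable patients and states that the study is not formally powered. No significance level, SD, effect size or replicate count is given.

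**2. Which tests are planned, and does a tumour-type shift reach them?** Write the response of sample i to regimen j as

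y_ij = regimen_j + d × type_i + e_ij,

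where type_i is 1 for the minority tumour type and 0 otherwise.

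- Paired t-test: y_i1 − y_i2 does not contain d.
- Repeated measures ANOVA: the sample effect, including d, is removed before regimens are compared. In simulation with an additive shift, its rejection rate stayed at about 5% (4.4% to 5.4%).
- Ranks within a sample, which feed Kendall's W: adding the same amount to every regimen leaves the ranks unchanged.

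These tests compare regimens. None of them tests variation between patients, and the groupings of samples are descriptive. The inter-patient criterion thus has no named test or level. A stand-in is needed to put a size on the problem.

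**3. Illustration with a stand-in test.** This is the F test for samples in a sample × regimen layout. It is not in the plan.

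Inputs: N = 50 samples (7.1, the maximum). Everything else is assumed: K = 5 regimens, residual SD 1, 5% level, share p of samples shifted by d residual SD, and no patient variation within a type.

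- Degrees of freedom: N − 1 = 49 and (N − 1)(K − 1) = 196. The 5% critical value is 1.419.
- Noncentrality: λ = K × N × p(1 − p) × d².
- Chance of significance: the upper tail of the noncentral F beyond 1.419.

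| p | d | λ | Chance of a significant result |
|---|---|---|---|
| 0.20 | 0.5 | 5 × 50 × 0.16 × 0.25 = 10 | 21% |
| 0.20 | 1.0 | 5 × 50 × 0.16 × 1 = 40 | 87% |
| 0.30 | 0.5 | 5 × 50 × 0.21 × 0.25 = 13.1 | 29% |
| 0.30 | 1.0 | 5 × 50 × 0.21 × 1 = 52.5 | 96% |

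Once tumour type is fitted, d leaves the between-sample comparison, λ = 0, and the chance is 5% in every row.

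**4. A second layout.** Take one regimen with three replicate cultures per patient (assumed) and a one-way F test for patients, simulated 4,000 times per setting. At d = 1, the pooled test was significant in 25%, 51%, 67% and 77% of studies for minority shares of 5, 10, 15 and 25 out of 50. Tested within tumour type, the rate was 4.4% to 5.7% over all settings. The size depends on the layout; the direction does not.

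**5. How plausible are the shares?** The documents do not state the expected mix. Section 1.2 puts glial tumours at 70% of adult malignant brain tumour diagnoses, so 20% to 30% non-glioma is not far-fetched, but it remains an assumption.

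**The case against.** **The percentages describe no test in the plan.** This is correct. They show what pooling does to a reasonable test of between-sample variation, not the error rate of the planned analysis. A reader might infer that the planned ANOVA or t-tests are inflated to 21% or 87%; step 2 shows that an additive shift does not touch them. That the inter-patient criterion has no defined test leaves it more open to case mix, not less.

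**Zero variation within a type is extreme.** This is also fair. Section 7.2.1 itself presupposes heterogeneous glioma response. With an assumed within-type patient SD of 0.5, the variance ratio is inflated by 1 + 5 × 0.25 = 2.25, and the stand-in test is significant in about 97% of studies at 50 samples and 91% at 35, with no tumour-type effect at all. Case mix would then rarely decide the result. But a pooled analysis cannot show which situation applies, and a within-type analysis can.

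**The rule has two halves.** Success also needs intra-patient variation. A reader might infer that tumour type alone can deliver a positive study; the documents do not support that.

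**The objective is not glioma-only.** In section 2.1, glioma qualifies the therapies, while the synopsis and sections 1.1 and 3.1 speak of primary brain tumours. It is tempting to read the pooled analysis as contradicting a glioma estimand, but no such estimand is set. What remains is a wording difference.

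**Excluded pathology.** A reader might infer that the plan deliberately analyses excluded tumours. Section 1.1 speaks of subtype, section 3.5 requires eligibility, and lymphoma and myeloma are excluded only when suspected. That is an ambiguity, not a stated policy.

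**Low stakes.** The study is a proof of concept and guides no treatment (1.3). This limits the severity but does not settle what a declared success would mean.

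**Conclusion.** The point holds for the inter-patient half of the success rule. Section 7.2.1 pools all eligible tumour types, names no tumour-type stratum or term, and accepts any significant inter-patient variation. Differences that pathology already reports can meet that half.

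The conclusion rests on the wording of sections 1.1 and 7.2.1. Its size rests on assumptions: with a stand-in F test, no variation within a type and 20% of samples shifted by 0.5 or 1.0 SD, a significant result appears in about 21% or 87% of studies instead of 5%. Real variation within types would reduce the practical effect of pooling. The point bears on interpretation, not on sample size or breadth of entry. It should be corrected before analysis, but it does not threaten the conduct of the study.

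**What to change.** 1. In section 7.2.1, base the inter-patient criterion on variation between patients within tumour type, with tumour type as a stratum or a single factor. Show the glioma subset separately and keep the pooled all-sample result as supportive.
2. State which test and significance level the inter-patient criterion uses.
3. Show results descriptively by IDH, by MGMT, and by newly diagnosed versus recurrent disease. With at most 50 samples, a joint model of type, grade, IDH, MGMT and recurrence would be too sparse.
4. Use one wording of the primary objective in the synopsis and section 2.1.
5. Reconcile section 1.1 with sections 3.5 and 3.6 on samples that pathology later shows to be of an excluded type.

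Broad inclusion can stay. The change needs plan wording and one stratum or factor from pathology data that section 3.3 already requires, with no new patients or procedures. The price is fewer samples per stratum, with some rare types too small to analyse alone, and a somewhat less favourable inter-patient result.

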## **1.2 Background and rationale**

Brain tumours are a large unmet need in the UK and worldwide. They are the leading cause of cancer death in the under-40's, with 12,500 new patients diagnosed annually in the UK and 88% dying within 5 years (1). The US faces similar problems, with 79,000 new cases and nearly 14,000 deaths annually (2). Of the malignant brain tumours, glial tumours are the most common, making up 70% of all adult malignant brain tumour diagnoses.

### **1.2.1 Current management of malignant glioma**

Malignant glioma includes grade 2-4 glioma, and forms the majority of primary brain tumours in adults. Glioma therapy depends on grade and subtype but broadly includes a combination of surgical resection, radiotherapy and chemotherapy.

Optimal treatment of glioblastoma (grade 4 glioma) consists of surgery, chemo-radiotherapy and chemotherapy with Temozolomide (3). For grade 3 astrocytoma, surgery, radiotherapy and adjuvant temozolomide are standard of care (4), and for oligodendroglioma, surgery, radiotherapy and PCV-based chemotherapy are standard of care. At relapse, therapy is typically further chemotherapy, either with the same agents, or previous unused chemotherapy. 3rd-line chemotherapy is poorly defined, but might include carboplatin or irinotecan, and may include bevacizumab.

Combined TMZ & Lomustine may be beneficial in MGMT methylated GBM, but apart from MGMT methylation, IDH mutation and 1p/19q co-deletion - which predict response to chemotherapy in general - there are no biomarkers to predict response to specific therapeutic agents.

### **1.2.2 Treatment response in malignant primary brain tumours**

Primary brain tumours have a 5-year survival rate of only 12%, and GBM has a median survival of 15 months with aggressive multimodal treatment (5). However, there is some evidence to support use of combined chemotherapy in newly diagnosed patients with GBM, uncertainty about chemotherapy regimen choice in grade 2 and 3 gliomas, and uncertainty about therapy choice at relapse across all gliomas.

### **1.2.2 Other primary brain tumours**

Outside of the gliomas, the commonest primary brain tumour is a grade 1 meningioma. We are not including these patients in the study, as the tumours have very good outcomes, and are unlikely to be possible to grow in our system. However, there are a range of other primary brain tumours, all of which are much rarer (e.g. ependymoma, grade 1 gliomas) which would all be eligible for inclusion in the study.

### **1.2.3 Predictive biomarkers of patient response**

The only good predictive biomarkers for glioma are IDH mutation status, 1p/19q codeletion and MGMT methylation. However, these all generally predict for chemotherapy responsiveness, rather than which therapy is best.

Pear Bio's test provides a potential avenue to test single agents and combination therapies prior to treatment selection to guide decision-making.

### **1.3 Benefit/risk assessment**

This is an observational study with patients receiving standard of care surgery. Samples collected from surgery will be used in Pear Bio's test, but they will not guide any treatment decisions. As such, there are no benefits to the patients taking part in this study.

This study will be used to conduct analytical validation of the patient stratification tool. The study data will be used to inform the design of future trials, which will be aimed at increasing patient response rates by using the test before systemic therapy starts to decide on the optimal treatment regimen(s) to use for an individual with glioma.

As surgery and blood collection are within routine care for resectable brain cancer, study-specific procedures do not pose significant risks to patients. A source of potential risk comes from collecting 40mL of matched whole blood per patient, which may go beyond routine care to satisfy study requirements. Possible risks associated with extra blood collection are a feeling of lightheadedness, dizziness and local bruising. However, this will be mitigated as patients with preoperative haemoglobin levels below 120g/L will not be recruited.

